					T	rue DLT ra	ate		
	10%	20%	30%	40%	50%	60%	70%	80%	90%
Probability of									
escalation	0.91	0.71	0.49	0.31	0.17	0.08	0.03	0.01	0.001

A minimum of 6 patients and a maximum of 12 patients will be enrolled to the phase I portion of the trial.

Phase II: The primary objective is to determine the overall response rate, defined as the rate or CR + CRi occurring at the end of 2 cycles of treatment. A total of up to 26 patients will be in the phase II part including patients who received the MTD dose level in the phase I portion and those enrolled in the phase II portion of the study. The target overall response (OR) rate is 60%. This regimen of the combination treatment will be considered worthy of further investigation if it elicits an increase in OR to 60% with

acceptable toxicity. A >15% drug-related grade 4-5 toxicity rate is considered unacceptable. Thus, interim monitoring rules, assuming the prior distributions below, were constructed that meet the following two conditions,

- 1) Stop if $Prob[p(OR, E) < 0.60 \mid data] > 0.975$, or
- 2) Stop if $Prob[p(TOX, E) > 0.15 \mid data] > 0.8$,

where p(OR, E) and p(TOX, E) are the true OR and toxicity rates for the combination treatment. The first rule provides for stopping the study if the data suggest that it is unlikely (i.e., probability < 2.5%) that OR rate of the combination treatment is greater than 0.6. The second condition will stop the study early if excessive therapy-related grade 4-5 toxicity (>15%) is highly probable (i.e., probability >80%) for the combination treatment. Monitoring for toxicity and futility will not begin until 6 patients have been evaluated, and cohort size for future evaluations is 2.

The monitoring rule for the toxicity rate, based on these assumptions and monitoring conditions above is found in Table 2. For example, accrual will cease if 2 or more patients experience toxicities among the first 6 patients. Toxicities will be continually monitored and will count towards this stopping rule if they occur while the patient is still on study.

Table 2. Stop accrual if there are this many drug-related grade 4-5 toxicities among the number of patients evaluated					
# patients evaluated	# patients with toxicities				
6	2-6				
8-10	3-10				
12-16	4-16				
18-20	5-20				
22-24	6-24				
26	Stop due to maximum sample size				

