Monitoring the OR rate, based on the above assumptions and monitoring conditions is found in Table 3. For example, accrual will cease if no patients experience an overall response in the first 6 patients treated.

Table 3. Stop accrual if there are th number of patients evaluated	is many response (i.e., # patients with overall response) among the	
# patients evaluated	# patients with overall response	
6	0	
8	0-1	
10	0-2	
12	0-3	
14	0-4	
16	0-5	
18	0-6	
20	0-7	
22	0-8	
24	0-9	
26	Stop due to maximum sample size	

Multc Lean Desktop (version 2.1.0) was used to generate the toxicity and futility stopping boundaries and the operating characteristics table (Table 3). In order to utilize the software for the design, a 60% constant rate and beta (1.2, 0.8) priors were assumed for the standard treatment response rate and experimental treatment response prior distribution, respectively. In addition, a 15% constant rate and beta (0.3, 1.7) priors were assumed for the standard treatment toxicity rate and experimental treatment toxicity prior distribution, respectively.

The probability of stopping the study early if the true OR of the combination treatment was 60% and the true toxicity rate was 15% was 39.24%. Probabilities of stopping early for high true toxicity rates (i.e., 40%) were 98.27% when the true OR was 60% and 99.79% when true OR rate was 30%.

True Toxicity Rate	True OR	Prob(stop the trial early)
0.10	0.30	0.9028
	0.40	0.6445
	0.50	0.3561
	0.60	0.2064
	0.70	0.1688
0.15	0.30	0.9256
	0.40	0.7278
	0.50	0.5070
	0.60	0.3924
	0.70	0.3636
0.2	0.30	0.9506
	0.40	0.8193
	0.50	0.6727
	0.60	0.5966
	0.70	0.5775
0.3	0.30	0.9861
	0.40	0.9490
	0.50	0.9076
	0.60	0.8861
	0.70	0.8808
0.4	0.30	0.9979
	0.40	0.9922
	0.50	0.9860
	0.60	0.9827
	0.70	0.9819

Secondary objectives include: the rate of minimal residual disease negativity by PCR for BCR-ABL1 transcripts, proportion of patients proceeding to ASCT, relapse-free survival, overall survival, and the safety of the combination regimen.

The investigator is responsible for completing toxicity/efficacy summary reports and submitting them to the IND office Medical Affairs and Safety Group for review. These should be submitted as follows:

- Phase I: A toxicity summary must be submitted after the first 3 evaluable patients, complete 1
 cycle of study treatment, and every 3 evaluable patients thereafter, IND office approval must be
 obtained prior to advancing/changing dose levels.

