- Phase II: A efficacy/toxicity summary must be submitted after the first 6 evaluable patients complete the second cycle of study treatment, and every 2 patients thereafter.

A copy of the cohort summary should be placed in the Investigator's Regulatory Binder under "sponsor correspondence".

Analysis Plan: Demographic/clinical characteristics and safety data of the patients will be summarized using descriptive statistics such as mean, standard deviation, median and range.

For the primary efficacy analysis, we will estimate the OR for the combination treatment (defined as the proportion of patients achieving CR or CRi after 2 cycles of treatment), along with the 95% credible interval. This regimen will be considered worthy of further investigation if an OR rate of at least 60% is achieved. Patients who drop out of the study before completing 2 cycles will be treated as "failures" for the primary analysis. The association between response and patient's clinical characteristics such as apoptotic protein expression, will be examined by Wilcoxon's rank sum test or Fisher's exact test, as appropriate.

The proportion of patient achieving CMR (as assessed by PCR for BCR-ABL transcripts) after 2 cycles of therapy will be estimated. The proportion of patients proceeding to ASCT and median time to ASCT will also be reported.

Kaplan-Meier curves will be used to estimate unadjusted OS and RFS distributions. Overall survival defined as the time from treatment initiation to death or last follow-up. RFS is defined as the time from the date of remission to relapse from CR or death from any cause whichever occurs first. Median OS and RFS as well as 1-year OS and RFS rates will be reported. Comparisons of time-to-event endpoints by important subgroups will be made using the log-rank tests.

Patients who enrolled in the phase I part of the trial who receive the MTD of venetoclax will be included in all efficacy analyses.

Toxicity type, severity and attribution will be summarized for each patient using frequency tables.

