Sample Size: We will treat up to 26 patients at the recommended phase II dose (including patients who received the MTD dose level in the phase I portion and those enrolled in the phase II portion of the study). For the efficacy endpoint, with a sample size of 26 patients, If the study is not stopped early and 26 patients have been treated and evaluated in the study, assuming 16 of the 26 patients achieve OR, then the 95% credible interval for OR rate will be (0.43,0.79).

Approximately 10 patients per year are expected to be enrolled. The total study duration is expected to be 5 years (3 years of new patient enrollment, plus an additional 2 years of follow-up).

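### Should Table 3 stop accrual once 16 responses in 26 patients can no longer be reached?

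*Combined protocol and SAP*

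**What the plan says.** All of this is in Section 10 of the combined protocol and SAP.

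- **Final benchmark (Analysis Plan).** "This regimen will be considered worthy of further investigation if an OR rate of at least 60% is achieved". The same paragraph makes estimation of the response rate, with a 95% credible interval, the primary efficacy analysis. Patients who leave before completing two cycles count as failures.
- **Sample size.** "We will treat up to 26 patients at the recommended phase II dose". The worked example uses the smallest count that meets the benchmark: "assuming 16 of the 26 patients achieve OR, then the 95% credible interval for OR rate will be (0.43,0.79").
- **Interim futility rule (Phase II paragraph).** Accrual stops when the posterior probability that the true response rate is below 0.60 exceeds 0.975. The plan explains it so: "The first rule provides for stopping the study if the data suggest that it is unlikely (i.e., probability < 2.5"%) that the true rate is above 0.6.
- **Table 3.** "Monitoring the OR rate, based on the above assumptions and monitoring conditions is found in Table 3". It stops at 0/6, 0-1/8, 0-2/10, 0-3/12, 0-4/14, 0-5/16, 0-6/18, 0-7/20, 0-8/22 and 0-9/24.
- **Timing of looks.** "A efficacy/toxicity summary must be submitted after the first 6 evaluable patients complete the second cycle of study treatment, and every 2 patients thereafter".
- **Accrual.** "Approximately 10 patients per year are expected to be enrolled".
- **Operating characteristics.** Only the probability of early stopping is tabulated. For example, the value when "the true OR of the combination treatment was 60% and the true toxicity rate was 15% was 39.24"%.

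**The concern.** Read together, the interim and final rules appear not to fit. A trial with 13 responses in 24 patients continues to 26 under Table 3, yet two further responses give only 15/26, below 60%. The plan does not discuss this region. The operating characteristics table hides it as well, since it shows early stopping but not how often the benchmark is met.

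At stake would be enrolling patients with relapsed or refractory disease after the one stated efficacy benchmark is out of reach, in a trial that also monitors for drug-related grade 4-5 toxicity. A reader might also take the low futility-stopping rate at a true response rate of 60% for a high chance of a positive result.

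**Working it through.** **1. Reproduce the plan's figures.** Inputs from Section 10: Beta(1.2, 0.8) prior for response and Beta(0.3, 1.7) for toxicity; looks at 6, 8, ..., 24; maximum 26.

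- Futility: stop at r responses in n if Pr(p < 0.60) > 0.975 under Beta(1.2 + r, 0.8 + n - r). All ten Table 3 limits reproduce. At 18 patients, for instance, 6 responses give 0.985 (stop) and 7 give 0.957 (continue).
- Toxicity: stop at t events in n if Pr(p > 0.15) > 0.8 under Beta(0.3 + t, 1.7 + n - t). All ten Table 2 limits reproduce.
- Early stopping, by exact enumeration with response and toxicity independent: at response 60% and toxicity 15% the result is 0.3924, as stated. The other cells checked also agree to four decimals.
- The interval for 16/26 under Beta(17.2, 10.8) is (0.431, 0.782), against the stated (0.43, 0.79). The 0.01 gap has no bearing here.

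**2. Which continuing states cannot reach the benchmark?** The smallest qualifying count is 16 (16/26 = 61.5%; 15/26 = 57.7%). It is out of reach when r + (26 - n) < 16.

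| n | Table 3 stops at | 16/26 out of reach at | Continuing but out of reach | Best finish |
|---|---|---|---|---|
| 16 | 0-5 | 0-5 | none | - |
| 18 | 0-6 | 0-7 | 7 | 15/26 |
| 20 | 0-7 | 0-9 | 8-9 | 14-15/26 |
| 22 | 0-8 | 0-11 | 9-11 | 13-15/26 |
| 24 | 0-9 | 0-13 | 10-13 | 12-15/26 |

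No such state exists at the earlier looks.

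**3. Do these states meet the plan's futility condition?** No. Pr(p < 0.60) is 0.957 at 7/18, 0.901 at 9/20, 0.815 at 11/22 and 0.705 at 13/24, all below 0.975. At 13/24 the 95% credible interval is 0.36 to 0.73, so the data have not excluded a true rate of 60%.

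**4. Does stopping there change any conclusion?** Count as success reaching 26 patients with at least 16 responses. At a true response rate of 60% this has probability 0.5207 under the futility rule alone, with Table 3 as it stands or with stopping extended to 0-7/18, 0-9/20, 0-11/22 and 0-13/24. The probability of never stopping for toxicity follows from the plan's own cells. The futility-only stopping rate at 60% is 0.0504, so:

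- toxicity 10%: (1 - 0.2064)/(1 - 0.0504) = 0.8357, and 0.5207 × 0.8357 = 0.435;
- toxicity 15%: (1 - 0.3924)/(1 - 0.0504) = 0.6399, and 0.5207 × 0.6399 = 0.333.

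Both are the same under either boundary, because no path through an added stop could have succeeded.

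**5. How many patients would be spared?** The 36% scenario is the blinatumomab response rate cited in Section 1. The lag is 10/365 × 56 days = 1.53 patients (two 28-day cycles) to 10/365 × 63 days = 1.73 patients (35-day first cycle). Enrolment at a stop is taken as min(26, n + lag).

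| True response rate | Toxicity 10%: no lag | with lag | Toxicity 15%: no lag | with lag |
|---|---|---|---|---|
| 36% | 1.5 | 1.1-1.2 | 1.2 | 0.9 |
| 40% | 1.9 | 1.4 | 1.5 | 1.1 |
| 50% | 2.0 | 1.3-1.4 | 1.5 | 1.0 |
| 60% | 1.0 | 0.6 | 0.8 | 0.4-0.5 |

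With the lag, the 24-patient look contributes only 0.01-0.06 patients per trial. Yet at response 60% and toxicity 10% it accounts for the rise in reported early stopping from 0.357 to 0.458, out of a total rise from 0.2064 to 0.4576.

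**The case for a change.** The strongest case for a change is that the extra stopping looks free. Success probabilities are untouched, no patients are added, and trials of a mediocre regimen end sooner. Nor is the region rare: under the futility rule alone, 50% of trials at a true rate of 50%, and 30% at 60%, pass the 24-patient look with 16/26 already unattainable. A reader would also learn something from seeing that a regimen truly at the 60% target meets the benchmark only 44% of the time at 10% toxicity.

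The arithmetic stands; the inference to a change does not.

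- The interim rule concerns the true rate and the benchmark concerns the observed rate. A lenient posterior futility rule beside a final benchmark is a recognised choice, and the plan states its threshold openly.
- Editing four Table 3 cells alone would introduce an error. The added stops fail the 0.975 condition from which the table is said to be derived, so a further stopping condition would be needed. The early-stopping table and its quoted percentages would also need recomputing: 39.24% becomes 58.47%, 98.27% becomes 98.82% and 99.79% becomes 99.99%.
- The last patients are not wasted. They inform the response-rate interval, which is the primary analysis, as well as molecular response, transplant rate, survival and safety. The plan does not give this as its reason for continuing, but the use is plain.
- The plan claims no power. A column of success probabilities would be informative, but it would correct no stated figure.

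**Conclusion.** No change is needed. From 18 patients on, Table 3 does allow accrual where 16/26 is unattainable, but it follows exactly from the rule the plan sets out, and the benchmark can be applied at the end without ambiguity. Stopping earlier would leave every efficacy conclusion as it is. It would spare roughly 0.4 to 1.4 patients per trial at true response rates of 36-60% and toxicity of 10-15%, or 0.8 to 2.0 if every response were known at once. Against that stands the loss of estimation, secondary-endpoint and safety data in a trial of at most 26 patients. Statisticians could reasonably choose either side.

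These sizes assume independent response and toxicity, looks exactly at 6, 8, ..., 24, uniform accrual of 10 per year and no pause while responses are awaited. The plan states the accrual rate but neither its uniformity nor whether accrual pauses.
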